a) Study A: Characterizing the determinants of upper airway obstruction

- 1) To determine the contribution of defects in upper airway function to the pathogenesis of airway obstruction at specific sites of pharyngeal collapse by characterizing upper airway pressure-flow/area relationships during DISE.

We hypothesize that increases in tissue compression and pharyngeal compliance will be associated with primary sites of airway obstruction at the base of tongue and nasopharynx, respectively.

- 2) To determine the impact of jaw thrust and mouth closure on functional determinants of upper airway obstruction at specific sites of pharyngeal collapse.

We hypothesize that jaw thrust and mouth closure will preferentially mitigate tissue compression and restore airway patency at the tongue base.

- 3) To examine effects of maxillo-mandibular restriction and tongue morphology on pharyngeal function during DISE.

We hypothesize that maxillo-mandibular restriction and that tongue size and fat content will predict the degree of pharyngeal compression and elevations in airway collapsibility.

b) ***Study B: Electrical Stimulation of Tongue Muscles**

- 1) To assess effects of stimulating the hypoglossal nerve on upper airway patency during DISE and on tongue morphology.

We hypothesize that hypoglossal nerve stimulation will lead to improvements in upper airway patency during DISE.

- 2) To assess whether craniofacial morphology predicts improvements in pharyngeal patency during DISE with stimulation.

We hypothesize that maxillo-mandibular restriction will be associated with diminished responses in airway patency to stimulation during DISE.

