Overnight sleep study will be used to characterize patients' sleep apnea. This test consists of a standardized array of non-invasive sensors applied to the head (EEG), chin and legs (EMGs), upper lip (airflow) the finger (oximetry), and chest/abdomen (respiratory effort, ECG). It records physiologic signals non-invasively that detect apneic episodes and characterize sleep/wake state.

b. Drug and device management

Propofol and equipment for conducting drug-induced sleep endoscopy will be procured and administered by trained endoscopy/operating room staff. The Inspire stimulator will have already been implanted as part of routine clinical care and will be operated by trained staff using the Inspire Programmer.

7. Study Statistics

Our primary independent variable is stimulation status (on versus off). Additional predictors of responses to stimulation will include measurements of tongue and craniofacial morphology.

a. The impact of these independent variables will be examined on the following primary outcome variables:

- Tidal airflow and related flow-surrogates for upper airway collapsibility
- Pharyngeal cross-sectional area in the velo- and oropharynx

b. Secondary outcome variables:

N/A

c. Statistical plan including sample size justification and interim data analysis:

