Using an ANOVA framework for estimating sample size for a 1x3 factorial design (Specific Aim A: complete responder, partial responder, and non-responder), we calculate the sample required to detect within-subject changes in upper airway function (e.g., the severity of upper airway obstruction during DISE as reflected by measurements of pharyngeal collapsibility, P_{CRIT}), based on published data demonstrating decreases in pharyngeal collapsibility (P_{CRIT}) of $\sim 3.5 \pm 2.0$ cmH₂O during stimulation ³⁴. This response accounts for $\sim 24\%$ of the total variance (η^2), which yields an effect size (f) of ~ 0.40 . Our data also demonstrate within-subject correlations of at least 0.5 for repeated P_{CRIT} measurements ^{69,70}. Using these parameters, we calculated that 15 subjects would be required to detect significant differences in each of 3 responder categories with an alpha of 0.05 and a power of 90%. To account for measurements in both sexes, subject attrition, and incomplete measurements, we propose an 'n' of 45 subjects to complete the protocol. We also plan to examine the effects of sex and BMI on this outcome, which will require an additional 30-60 subjects (total n = 100) for the entire protocol. This sample size will allow us sufficient power to detect substantial effects of stimulation on tongue morphology (Specific Aim B) and effects of craniofacial structures on tidal airflow and markers of airway collapsibility (Specific Aim C).

d. Early stopping rules.

- This is a low-risk study designed to examine underlying mechanisms of action of lingual and hypoglossal nerve stimulation treatment in patients with obstructive sleep apnea. Since the protocol will involve temporarily stopping HGNS treatment for 5 days, one risk includes excessive daytime sleepiness. We have attempted to minimize subject risk with the strict exclusion criterion, "Patients who have fallen asleep while during resulting in an accident or 'near miss' accident within 1 year prior to device implantation." In addition, we will advise patients against driving and operating heavy machinery during this 5-7 night washout period and we will perform a check-in call after the first 2 nights without therapy. We will specifically ask patients if they have fallen asleep while driving, and will withdraw any patients answering yes. We also recognize and inform each subject of his/her right to withdraw from the clinical study at any time.

8. Risks

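### The 90% power claim in SAP 7c assumes one effect in all three responder categories and does not match the design, and no test of differing response (objective B2) is stated or sized

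*SAP*

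**What the plan says.** Section 7 of the SAP opens with the comparison of interest: "Our primary independent variable is stimulation status (on versus off"), and adds tongue and craniofacial measurements as further predictors of response.

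Section 7c then sizes the study for a "1x3 factorial design (Specific Aim A: complete responder, partial responder, and non-responder"). The target is within-subject: "we calculate the sample required to detect within-subject changes in upper airway function", with the critical closing pressure (PCRIT) as the example. One published average is used, a fall of about 3.5 ± 2.0 cmH2O with stimulation. This is said to explain about 24% of the variance, "which yields an effect size (f) of" about 0.40. The calculation also uses "within-subject correlations of at least 0.5", alpha 0.05 (sidedness not given) and 90% power. The result is that "15 subjects would be required to detect significant differences in each of 3 responder categories". The total is set at 45 and then raised to 100 for sex and BMI. Power for the tongue-morphology and craniofacial aims is asserted without a figure.

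The second Study B objective in Section 2b is "To assess whether craniofacial morphology predicts improvements in pharyngeal patency during DISE with stimulation", with the hypothesis that a restricted maxillo-mandibular frame goes with a smaller response. No objective in Section 2 mentions responder categories, and the SAP does not define them.

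**The concern.** There are three difficulties.

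- **One effect for all.** The categories are named for differing response, yet the same average change is assumed in each. The 90% is least credible for non-responders.
- **A within-subject number for a between-subject factor.** A patient belongs to one responder category. A calculation for repeated levels within a patient does not give the power to compare categories, and it is not a two-sided on/off test within one category either.
- **No contrast for B2.** Whether morphology predicts improvement is a question of effect modification. It needs a difference in change between patients, that is, an interaction of stimulation with the predictor. Section 7c neither states nor sizes one.

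Section 9 of the SAP says the work should help identify the patients for whom stimulation is indicated. A result that rests on significance in one category and not in another would not support that. A power claim that does not belong to the comparison gives false assurance about it.

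**Working it through.** **Inputs from 7c:** f = 0.40; correlation ρ = 0.5; alpha 0.05; power 90%; 15 per category; 45, then 100 in total; mean change 3.5 with ± 2.0 cmH2O. Section 4b expects about 20% not to complete all visits, so 100 × 0.8 = 80.

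**Step 1: reproduce the 15.** Within-factor repeated-measures ANOVA, one group, m levels: λ = n·m·f²/(1−ρ), with m−1 and (n−1)(m−1) degrees of freedom.
- m = 3, n = 15: λ = 15 × 3 × 0.16/0.5 = 14.4, df 2 and 28, power 90.6%. With n = 14, 88.2%. The plan's 15 is recovered.
- m = 2 (on/off, two-sided), n = 15: λ = 15 × 2 × 0.16/0.5 = 9.6, df 1 and 14, power 82.1%. With n = 18, 89.2%; with n = 19, 90.9%. So 19 are needed.
- One-sided paired t: dz = 2f/√(2(1−ρ)) = 0.80/1 = 0.80; noncentrality 0.80 × √15 = 3.10; power 90.3% at n = 15.

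The 15 therefore comes from three repeated levels in one group, or from a one-sided on/off test. Neither compares categories.

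**Step 2: the uniform effect in non-responders.** Two-sided paired t, n = 15, taking 2.0 as the SD of change. The two smaller means are assumptions for illustration.

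| Mean change in non-responders (cmH2O) | dz | Power |
|---|---|---|
| 3.5 | 1.75 | >99.9% |
| 1.0 | 0.50 | 43.8% |
| 0.5 | 0.25 | 14.7% |

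If the mean really is 3.5 in all three categories, there is no difference between them to find, and a between-category test rejects at the 5% level only.

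**Step 3: what a between-category test can detect.** One-way ANOVA on the change score, three equal categories: λ = N·f², df 2 and N−3. For equally spaced means the SD of the means is spread/√6, so spread = f × √6 × SD. With SD 2.0:

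| N | f for 90% power | Spread, largest to smallest mean | Power at f = 0.40 |
|---|---|---|---|
| 45 | 0.550 | 0.550 × 2.449 × 2.0 = 2.7 cmH2O | 63.5% |
| 80 | 0.406 | 2.0 cmH2O | 89.1% |
| 99 | 0.363 | 1.8 cmH2O | 94.9% |

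(99 stands for 100 split equally in three; 80 is treated as nearly equal thirds.) On this scale f = 0.40 is a spread of 0.40 × 2.449 × 2.0 = 1.96 cmH2O.

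**The case against.** The strongest reply is that 7c contains a sizing sentence, not an analysis instruction. A reader might infer that the plan prescribes three separate on/off tests and so cannot show that response differs between patients. The document does not support that. The Study Summary gives ANOVA as the method, Section 7 names predictors of response, Section 2b states a hypothesis about diminished response, and 7c intends to look at sex and BMI. The data collected would allow an interaction test. All of this stands. Were three separate tests used, identical true effects would give a mixed pattern of significance with probability 1 − 0.821³ − 0.179³ = 44%, or 27% at 90% power each. That is a hazard of one reading, not a property of the plan.

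It can also be said that a category-by-stimulation interaction of f = 0.40 on the repeated-measures scale has 99.8% power at 45 (λ = 45 × 2 × 0.16/0.5 = 28.8). The figure is correct, but on the change score it equals f = √(2 × 0.16/0.5) = 0.80, a spread of 0.80 × 2.449 × 2.0 = 3.9 cmH2O. That exceeds the average effect of 3.5 itself, so it gives no comfort for moderate differences.

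The planned total is 100, so figures at 45 alone would be unfair to the study; this stands, and the spread is given at all three sizes. Finally, with the categories undefined, a PCRIT fall of 3.5 in non-responders is implausible but not impossible, for instance if category is taken from the sleep study and the outcome from DISE. This stands too.

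**Conclusion.** The point holds in this form: the plan states and sizes no test that would show differing response, and its only calculated power figure fits neither the between-subject categories nor a two-sided on/off test. At the plan's own f and ρ, 15 per category gives about 82% two-sided and not 90%. For a comparison of categories, 90% power needs a spread of about 2.7 cmH2O at 45, 2.0 at 80 and 1.8 at 99.

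Assumptions: the 82% rests on f = 0.40 and ρ = 0.5 as stated. It is not the power for 3.5/2.0 read as mean and SD of change, which is above 99.9%. The plan's inputs do not agree on this, since a variance share of 24% would itself give f = √(0.24/0.76) = 0.56; that is a separate matter. The spreads assume equal categories, equally spaced means and an SD of change of 2.0, although the SAP does not say what the ± denotes. Unequal categories would detect less.

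**What to change.** In 7c:

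1. Name the overall on/off change as the test for objective B1.
2. Name the interaction of stimulation with morphology as the test for B2, and with responder category as well if categories are kept. Report each as a difference in change with a confidence interval.
3. If categories are kept, define them independently of the DISE outcome.
4. Delete the per-category 90% claim with its uniform effect, or restate it as about 82% two-sided at 15 for f = 0.40 and ρ = 0.5.
5. Say what the ± 2.0 denotes, and give the detectable between-category spread at the n expected to be analysed: under the assumptions above, about 2.7 cmH2O at 45, 2.0 at 80 completers, 1.8 at 99. A continuous morphology measure needs its own detectable difference.

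The cost is wording and a less favourable power figure. No extra patients or measurements are required.

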Prior to sleep, patients will undergo facial measurements. A digital camera with laser pointers will be used to capture a series of craniofacial photographs (frontal, profile and neck extended) and intra-oral photographs (junction of the hard and soft palate, airway, or base of tongue). The participant will then perform serial tongue force exercises using a bulb behind their front teeth to assess tongue force.

Thereafter, responses to stimulation will be assessed during DISE with ultrasound measurements of tongue morphology and with measurements of pharyngeal patency during DISE ([Visit #4](#)). Responses in pharyngeal patency will be assessed with video endoscopy, pharyngeal manometry, and tidal airflow monitoring (Studies A+B) while briefly stimulating tongue muscles during DISE (Study B only).

COVID-testing for each of the visits/assessments listed above will be required per departmental guidelines/regulations.

Each of the specific study procedures shown in the Study Design are described immediately below.

Study Flow Diagram

Abbreviations:

- OSA: Obstructive Sleep Apnea
- DISE: Drug-Induced Sleep Endoscopy
- Hx/PE: History/Physical Exam
- HGNS: Hypoglossal Nerve Stimulation

ASSESSMENT #1: CRANIOFACIAL
MRI SCAN (Visit #2)
 • Bony morphology
 • Tongue Size
 • Fat content
 • Pharyngeal lumen size

+

ASSESSMENT #2: OVERNIGHT
SLEEP STUDY (Visit #3)
SPLIT PSG: $\frac{1}{2}$ baseline, $\frac{1}{2}$ HGNS (settings unchanged from clinical optimization)

+

ASSESSMENT #3: DISE STUDY
(Visit #4)
 • Pharyngeal Videoendoscopy
 • Tidal Airflow and CPAP changes
 • Pharyngeal Manometry
 • Submental Ultrasound

	Visit 1: Screening/ Consent*	Visit 2: MRI	Visit 3: Sleep Study*	Visit 4: DISE
Informed Consent	X			
History and Physical	X			
Questionnaires	X			

**Study A (Baseline
Protocol)**

DISE				X
Pharyngeal Manometry				X
Tidal Airflow Monitoring				X
Airflow Manipulation				X
Ultrasound				X

**Study B (Stimulation
Protocol)**

MRI		X		
Digital Morphometrics			X	
Tongue Force			X	
In-Lab Sleep Study			X	
DISE				X

Pharyngeal Manometry				X
Tidal Airflow Monitoring				X
Airflow Manipulation				X
Ultrasound				X
Nerve Stimulation			X	X

*The screening/consent visit may occur during the first scheduled assessment (MRI, PSG, or DISE) to facilitate scheduling and reduce patient burden.

Visit #1: Clinical Evaluation

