1. **Baseline Questionnaires:** Standard screening questionnaires will be administered initially at the time subjects are screened and consented. These questionnaires will assess several demographic, anthropometric, and physical health domains (see attached questionnaires). We will administer the standard Sleep Surgery clinical questionnaire which includes ESS, ISI, FOSQ-10, NOSE, sleep quality, snoring, etc. We will perform an Inspire device download to evaluate study eligibility (therapy compliance), and record their treatment settings. Patients without the most recent Inspire remote will be provided with one.

Visit #2: Overnight Sleep Study, Digital Morphometrics, Tongue Force Assessment

1. **Sleep study monitoring (polysomnography):** Standard monitoring of sleep will occur during Visit #2. For patients opting for Study A only, the sleep study may have already been performed as part of routine clinical care. For Study B, overnight nocturnal recordings will be performed in our sleep laboratory and will follow the same procedures (#1-5) outlined in Visits #3-4 below. The study will include monitoring of EEG, submental EMG, EOG, S_pO_2 , tidal airflow, thoraco-abdominal efforts, and body position. Recordings will be archived on an institutionally secured and managed network drive and accessible only to study personnel. Recordings will be accessed via a HIPAA secured web portal. Patients will be required to wash out from therapy between 5-7 days prior to PSG, i.e. they cannot use HGNS or other therapies during this time. A split night study will be performed (partially with HGNS, partially without). HGNS will not be titrated, i.e. we will use the settings optimized by clinical care prior to study participation. Patients must have a minimum of one hour of supine non-REM stage 2 sleep during both the baseline and treatment (with HGNS) assessments. If patients are unable to meet these criteria, they will not proceed with DISE.

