a. Medical risks, listing all procedures, their major and minor risks and expected frequency.

Baseline Questionnaires: These surveys acquire information that is routinely collected in the process of enrolling participants in clinical studies. There are not any significant physical risks with these procedures. As with all medical information, there is always the risk of psychological distress if personal health information is not held confidential. In order to minimize this risk, electronic PHI will be stored in a password-protected database (REDCap), and written information will be stored in locked files or file-rooms when not attended by study personnel.

Therapy Washout: Patients participating in Part B will undergo a 5-7-night therapy washout, i.e. they will not use Inspire for treatment of obstructive sleep apnea during this period. Untreated OSA increases the risk for excessive daytime sleepiness and consequently, motor-vehicle accidents. We have attempted to minimize subject risk with the strict exclusion criterion, "Patients who have fallen asleep while driving resulting in an accident or 'near miss' accident within 1 year prior to device implantation." In addition, during the patient consent (Visit 1), we will advise the patient against driving while sleepy. We will also perform a check-in call after 2 nights off therapy.

Ultrasound procedure for tongue imaging: Ultrasound is a non-invasive, inexpensive, and easy way to examine the morphology of the tongue and its response to stimulation. There is minimal discomfort associated with examination.

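### Sections 7d and 8a give driving advice of different scope for the same 5-7 night washout, and the narrower wording is the one tied to consent

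*SAP*

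**What the plan says.** Section 7d (Early stopping rules) names excessive daytime sleepiness as a risk of stopping therapy and lists the safeguards. Besides the entry exclusion, it says "we will advise patients against driving and operating heavy machinery during this 5-7 night washout period". It then schedules one telephone contact: "we will perform a check-in call after the first 2 nights without therapy". The next sentence reads: "We will specifically ask patients if they have fallen asleep while driving, and will withdraw any patients answering yes".

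Section 8a (Medical risks, Therapy Washout) covers the same washout and repeats the entry exclusion. On driving it says: "In addition, during the patient consent (Visit 1), we will advise the patient against driving while sleepy". On follow-up it says: "We will also perform a check-in call after 2 nights off therapy". The paragraph ends there.

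Two other places bear on when the advice is given. The Visit #2 procedures in section 4a place the washout before the sleep study: "Patients will be required to wash out from therapy between 5-7 days prior to PSG". The footnote to the visit table in section 4a says: "The screening/consent visit may occur during the first scheduled assessment (MRI, PSG, or DISE) to facilitate scheduling and reduce patient burden".

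**The concern.** The study itself creates the hazard, by stopping a treatment that participants were using successfully. Section 8a is explicit about the consequence: "Untreated OSA increases the risk for excessive daytime sleepiness and consequently, motor-vehicle accidents". Section 9 anticipates no direct benefit to participants. The entry exclusion looks back to the year before implantation, so it says nothing about what happens during the washout. For those nights the specific safeguards are the driving advice, the check-in call and the withdrawal rule.

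If the advice is worded in two ways, staff cannot tell from the document which to give. Section 8a ties its wording to a moment of delivery, the consent visit; section 7d gives no occasion for its wording. The narrower text is therefore the one more likely to reach the participant. It also leaves the decision to the patient's own sense of sleepiness.

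**Working it through.** No sample size, power or error-rate figure is involved. The check is a comparison of the two texts, plus one count of nights.

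**Step 1. Is it the same washout?** Yes. Sections 4d, 7d and 8a all give 5-7 nights off therapy, the Visit #2 procedures give 5-7 days, and 8a limits it to Study B.

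**Step 2. Compare the safeguards.**

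| Element | Section 7d | Section 8a |
|---|---|---|
| Driving | Advised against throughout the washout | Advised against when sleepy |
| Heavy machinery | Advised against | Not mentioned |
| When the advice is given | Not stated | At consent (Visit 1) |
| Check-in call after 2 nights | Yes | Yes |
| Question on falling asleep while driving | Yes | Not mentioned |
| Withdrawal if the answer is yes | Yes | Not mentioned |
| Entry exclusion for a sleep-related accident or near miss | Yes | Yes |

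The two sections agree on the call and the exclusion. They differ on the scope of the driving advice, and 8a lacks three further elements: machinery, the question and the withdrawal rule.

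**Step 3. Does the difference change what a patient may do?** Take a patient on the fourth day off therapy who feels alert. Under 7d the advice is not to drive. Under 8a the advice does not apply. For a patient who feels sleepy, both sections say not to drive. The gap is therefore driving while subjectively alert, and any use of machinery.

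**Step 4. When is the advice given, relative to the washout?** The footnote, read literally, allows consent at the sleep study, which comes after the washout. Other text points the other way:
- Section 4a says participants are first consented and screened, and go on to the assessments once the inclusion criteria are met.
- Section 5 requires a pregnancy test before enrollment and gives the stopping of treatment as a reason, which makes sense only if enrollment comes first.
- The Visit #1 procedures include the device download that checks therapy compliance for eligibility.
- Section 7d has staff calling patients after night 2 and withdrawing some of them, so they are already participants.

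Consent before the washout is the evident intention, but no sentence states it.

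**Step 5. How many nights follow the call?** Nights remaining = washout length − 2.
- 5 nights: 5 − 2 = 3, and 3/5 = 60%.
- 7 nights: 7 − 2 = 5, and 5/7 = 71%.

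These are counts of nights, not of risk. They show how much of the washout relies on the advice alone if the question is asked only at that call.

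**The case against.** The strongest reply is that nothing here conflicts. Section 8a does not say that its advice is the whole of the advice, and a patient who obeys 7d also obeys 8a. Both can be carried out. That stands: the difference is one of scope, and calling the sections contradictory would go too far. It does not remove the point, because the converse fails. A patient who obeys 8a may breach 7d, and 8a is the section that describes the consent conversation.

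A reader might also infer three stronger things, none of which the document supports.

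- *That participants could be warned only after the washout is over.* The footnote permits this on a literal reading, but the four places in step 4 point to consent and enrollment first. A clarification is justified; a claim that a late warning is planned is not.
- *That the withdrawal question has no occasion, so that events late in the washout would be missed.* The question directly follows the sentence on the night-2 call, and that call is its natural place. The text also does not exclude asking again later.
- *That one call is too few.* Nothing in the document shows this. A second call is a preference.

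Finally, the consent form is not available here, so it may already carry the stricter wording. That limits what can be said about what participants are told. It does not reconcile the two sections.

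**Conclusion.** The point holds as a participant-safety inconsistency. For one 5-7 night washout, 7d advises against all driving and machinery use, while 8a, describing consent, advises against driving when sleepy and leaves out machinery, the driving question and the withdrawal rule.

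Its size cannot be put as a risk, because the document gives no rate of sleepiness or accidents off therapy. It has no bearing on sample size, power or error rates. It is a modest point, worth acting on because the harm is serious and the correction is nearly free.

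The conclusion rests on two assumptions: that both sections describe the same washout, which their shared length and purpose make clear, and that staff would take the consent advice from 8a, which is likely but cannot be confirmed without the consent form. Taking 7d as the text to keep is a judgement in favour of the safer wording; the document does not say which was intended.

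**What to change.** 1. In section 8a, replace the advice about driving when sleepy with the full 7d advice: no driving and no heavy machinery for the whole 5-7 night washout.
2. In the same place, state that consent and this advice come before the first night off therapy. Add a matching clause for Study B to the visit-table footnote. Consent could still be combined with the MRI or DISE visit if that visit precedes the washout.
3. In section 8a, repeat that the call after night 2 asks about falling asleep while driving, and that a yes leads to withdrawal.
4. Check that the consent form carries the same advice.

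Optionally, ask the driving question again on arrival for the sleep study, which needs no extra contact, or at a second call late in the washout. Neither is needed to resolve the inconsistency.

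The cost is a few lines in section 8a and one clause in a footnote. For Study B, consent could no longer be combined with a sleep study that follows the washout. The stricter restriction at consent may deter a few participants; the document gives no figure from which to estimate how many.
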